6.2 Baseline Blood Pressure

Target population	:	Full Analysis Set
Group	:	Placebo, Zilebesiran 300 mg, Zilebesiran 600 mg, Total zilebesiran, Overall Total
Analysis Items	:	24-hour ABPM (mmHg) (Systolic blood pressure, Diastolic blood pressure), Daytime ABPM (mmHg) (Systolic blood pressure, Diastolic blood pressure), Nighttime ABPM (mmHg) (Systolic blood pressure, Diastolic blood pressure), OBP (mmHg) (Systolic blood pressure, Diastolic blood pressure), HBPM (mmHg) (Systolic blood pressure, Diastolic blood pressure)
Content of analysis	:	
 Calculate the summary statistics of baseline Systolic blood pressure and Diastolic blood pressure by 24-hour ABPM, Daytime ABPM, Nighttime

		ABPM, OBP and HBPM by groups.
Definitions	:	
 Daytime is defined as 6 am to 9:59 pm and nighttime is defined as 10 pm to 5:59 am.

6.3 Summary of Medical/Surgical History

Target population	:	Safety Analysis Set
Group	:	Placebo, Zilebesiran 300 mg, Zilebesiran 600 mg, Total zilebesiran, Overall Total
Analysis Items	:	Medical/Surgical History
Content of analysis	:	
 The number and percentages of patients with at least one medical/surgical history will be summarized by groups. The number and percentage of patients who has medical/surgical history will be summarized by groups, System organ class, High level term and Preferred Term.
Definitions	:	
 The denominator is the target population by groups In the tabulation of medical/surgical history, if the same patient had multiple medical/surgical history corresponding to the same same System organ class, High level term, Preferred Term code when counting the Preferred Term, same System organ class, High level term when counting High level term, same System organ class when counting System organ class, the data will be tabulated as one medical/surgical history

6.4 Study Drug Administration

Target population	:	Safety Analysis Set
Group	:	Placebo, Zilebesiran 300 mg, Zilebesiran 600 mg, Total zilebesiran, Overall Total
Analysis Items	:	Study Drug Administration (Yes/No), Full dose successful Administration (Yes/No), Total duration of study exposure (days), and Dose Administered (continuous data)
Content of analysis	:	
 For Study Drug Administration and Full dose successful Administration, the number of patients and percentage will be calculated by groups. Calculate the summary statistics of Total duration of study exposure (day) and Dose Administered by groups.
Definitions	:	
 The denominator of proportions is the target population by groups.

7. Efficacy Evaluation

7.1 SBP and DBP

7.1.1 Summary of All Collected ABPM/OBP

Target population	:	Full Analysis Set
Analysis	:	SBP, DBP by ABPM and office blood pressure

Items		
Group	:	Placebo, Zilebesiran 300 mg, Zilebesiran 600 mg, Total zilebesiran, Overall Total
Time of analysis	:	Refer to section 2.8.1
Content of analysis	:	
 • Calculate the summary statistics of measurement value, change from baseline for each parameter by groups and analysis time points.

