3.3. Justification for Dose

Zilebesiran will be administered as a single dose of 300 or 600 mg SC in this study. These doses of zilebesiran have been selected for further evaluation in a planned Phase 2 study that will inform the doses selected for the Phase 3 program.

These doses were selected based on data from Study 001 and Study 002 that showed robust and durable reduction in serum AGT at these dose levels. Single and multiple doses of zilebesiran up to 800 mg in Study 001 and up to 600 mg in Study 002 were found to have acceptable safety profiles and lead to clinically meaningful reductions in 24-hour mean SBP by ABPM.

- In Study 001 Part A, single ascending doses of zilebesiran from 10 to 800 mg showed dose-dependent reductions in serum AGT and 24-hour mean SBP assessed by ABPM. Zilebesiran also demonstrated an acceptable safety profile at all dose levels. Based on Study 001 results, zilebesiran dose regimens of 150 mg q6M, 300 mg q6M, 600 mg q6M, and 300 mg q3M zilebesiran were selected to be evaluated in Study 002.
- In Study 002, a single dose of 300 or 600 mg zilebesiran (q6M regimens) showed clinically and statistically significant reductions in 24-hour mean SBP by ABPM compared to placebo at Month 3 (LS mean reductions of 16.7 mmHg for 300 mg and 15.7 mmHg for 600 mg) that were sustained through Month 6 (LS mean reductions of 14.5 mmHg for 300 mg and 14.2 mmHg for 600 mg). A dose-dependent reduction from baseline in serum AGT over time was observed across all the zilebesiran dose levels.
- For the proposed dose levels in this study, median reductions in serum AGT were 98.1% and 98.8% at Month 3 and 96.1% and 97.8% at Month 6 for the zilebesiran 300 and 600 mg doses, respectively. A log-linear relationship between reductions in serum AGT and change from baseline in 24-hour mean SBP by ABPM was observed in Study 002 leveraging data from all doses. Both regimens had acceptable safety profiles.

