Accordingly, dose levels of 300 and 600 mg were selected for Japanese patients in this study to generate safety, tolerability, efficacy, PD, and PK data to facilitate demonstration of comparability of systemic exposure and PD (serum AGT) in Japanese patients with non-Japanese patients at therapeutic dose levels used in ongoing studies and planned to be used in subsequent studies. Changes in blood pressure will also be evaluated to assess whether blood pressure reduction in Japanese patients is within the range of blood pressure reduction observed in non-Japanese patients.

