7.1. Determination of Sample Size

The planned enrollment for this study is 36 patients, each treatment arm will include 12 patients. The sample size estimate is not based on the primary endpoint, which is a safety endpoint. Instead, sample size was estimated based on the secondary endpoint of percent change in AGT from baseline to Month 3 in Study 001. In Study 001, standard deviation (SD) for the percent change from baseline to Week 12 (Month 3) in the pooled zilebesiran arms was 42%. Assuming an SD of 0.42, the proposed sample size will provide more than 90% power to detect a 50% difference in percent AGT reduction at Month 3 between zilebesiran and placebo at a significance level of 0.05 (2-sided).

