7.2.4. Efficacy Analyses

Descriptive statistics will be provided for SBP and DBP summarizing the observed values and changes from baseline over time. Blood pressure analysis measured by ABPM, office blood pressure, and HBPM will be conducted using the Full Analysis Set.

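### The plan compares blood pressure reduction with placebo-corrected LS means from another study but produces only unadjusted per-arm summaries

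*SAP*

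**What the plan says.** Protocol 3.3 closes by saying that changes in blood pressure will be evaluated "to assess whether blood pressure reduction in Japanese patients is within the range of blood pressure reduction observed in non-Japanese patients". For the two doses under study, the same section cites 24-hour SBP results from Study 002. These are effects against placebo at Month 3, "LS mean reductions of 16.7 mmHg for 300 mg and 15.7 mmHg for 600 mg", with 14.5 and 14.2 mmHg at Month 6.

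The planned analysis is narrower. Protocol 7.2.4 states: "Descriptive statistics will be provided for SBP and DBP summarizing the observed values and changes from baseline over time". SAP 7.1.1 reads: "Calculate the summary statistics of measurement value, change from baseline for each parameter by groups and analysis time points". SAP 7.1.2 repeats this for data censored for escape medication. SAP 4.1.1 fixes the statistics as n, mean, SD, SEM, median, minimum and maximum, shown for placebo, each dose, total zilebesiran and overall total. The rest of SAP 7.1 adds day/night summaries, responder counts, home readings, plots and a table of escape use. Neither document plans a between-arm difference, a confidence interval or a model for blood pressure.

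For AGT, Protocol 3.3 cites median reductions within arm: 98.1% and 98.8% at Month 3, 96.1% and 97.8% at Month 6. SAP 8.1 summarises percent change by arm. The sample size in Protocol 7.1 rests on a different quantity, the Month 3 contrast of active drug with placebo: "Assuming an SD of 0.42, the proposed sample size will provide more than 90% power to detect a 50% difference in percent AGT reduction".

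**The concern.** The aim and the output are on different scales. An arm's mean change from baseline contains the drug effect, the placebo response and regression to the mean. The last is to be expected because entry requires a 24-hour mean SBP of at least 130 mmHg on the most recent recording (Protocol 4.1 and 6.2.1), and SAP 4.1.2 takes the last recording before dosing as baseline. The Study 002 figures have placebo removed and are model-based. Setting a raw arm mean beside them compares unlike quantities.

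With 12 patients per arm, chance differences in baseline also matter, and no planned output adjusts for them. The choice of dataset is open too: SAP 2.6.1 offers all-collected and escape-censored data without saying which serves this comparison, while Protocol 3.5 leaves the sponsor unblinded to assignment. What is at stake is whether the statement about Japanese patients rests on a prespecified, like-for-like estimate with its uncertainty shown, or on an informal reading of arm means.

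**Working it through.** **Inputs.** Protocol 7.1: "The planned enrollment for this study is 36 patients, each treatment arm will include 12 patients". The documents give no SD for blood pressure change and no baseline/follow-up correlation. I assume an SD of change of 10, 12 or 15 mmHg and r = 0.5.

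**The plan's own figure (AGT).** With difference 0.50, SD 0.42 and two-sided 0.05, for pooled zilebesiran (24) against placebo (12): 0.50 / (0.42 × √(1/12 + 1/24)) = 3.367, and 3.367 − 1.960 = 1.407, so power is 92.0% (normal) or 90.5% (t). The stated figure of more than 90% reproduces on the pooled contrast. For one dose against placebo (12 v 12) the power is 83.0% or 79.6%. Either way, the planning quantity is a difference from placebo that no AGT table estimates.

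**Unadjusted difference in blood pressure change, one dose against placebo.**
- Half-width = t(0.975, 22) × SD × √(2/12) = 2.074 × SD × 0.408.
- SD 10 / 12 / 15 gives 8.5 / 10.2 / 12.7 mmHg.
- This interval can be worked out by hand, because n, mean and SD are tabulated for every arm.

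**Gain from baseline adjustment.** The variance ratio of ANCOVA to change score is s_F²(1 − r²) / (s_B² + s_F² − 2·r·s_B·s_F), where s_B and s_F are the baseline and follow-up SDs. At r = 0.5:

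| s_B, s_F (assumed) | Ratio | Variance reduction |
|---|---|---|
| equal | (1 + r)/2 = 0.75 | 25% |
| 10, 12 | 108/124 = 0.87 | 13% |
| 8, 12 | 108/112 = 0.96 | 4% |

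The lower rows are plausible because the entry threshold tends to shrink baseline variance.

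**Adjusted half-widths.** A three-arm ANCOVA has 36 − 4 = 32 degrees of freedom, so t = 2.037. The half-width is 2.037 × 0.408 × SD × √ratio, ignoring the small loss from estimating the slope.
- Ratio 0.75: 7.2 / 8.6 / 10.8 mmHg.
- Ratio 0.96: 8.2 / 9.8 / 12.2 mmHg.
- Part of this narrowing comes from pooling variance over three arms: unadjusted at 33 df, SD 10 already gives 8.3 rather than 8.5.

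**Chance baseline imbalance.** The SD of the difference in baseline means is s_B × √(2/12), or 3.3 to 4.9 mmHg for an assumed s_B of 8 to 12.

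**Reading against the benchmark.** Suppose the 300 mg estimate equalled 16.7 mmHg exactly. At SD 12 the interval would be 16.7 ± 10.2 = 6.5 to 26.9 unadjusted, and at best 16.7 ± 8.6 = 8.1 to 25.3 adjusted.

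**The case against.** The main defence is that the study is openly descriptive. Its primary endpoint is safety, Protocol 7.2 rules out formal testing, and the blood pressure comparison appears in the dose justification and not in either objectives table. This stands as to weight: the gap is between one stated aim and the output, and no planned test or primary analysis is affected. It does not remove the point, because estimation with an interval and no p-value is fully compatible with a descriptive plan.

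Several stronger readings are tempting, and the documents do not support them.
- A reader might infer that AGT suffers equally. It does not: the cited AGT benchmarks are within-arm medians, and SAP 8.1 with 4.1.1 yields that statistic.
- A reader might infer that no interval is obtainable. An unadjusted one is; only the adjusted estimate needs patient-level data.
- A reader might infer that regression to the mean biases any comparison. It affects raw arm changes, but in expectation it cancels once the placebo change is subtracted.
- A reader might infer that adjustment is worth a third more patients (1/0.75 = 1.33). That holds only with equal baseline and follow-up variances at r = 0.5.
- A reader might infer that randomisation is unstratified. Protocol 3.4 names no strata, but SAP 2.3 defers to a separate plan that is not available here.

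**Conclusion.** The point holds for blood pressure. Protocol 3.3 sets a comparison with non-Japanese results, the 24-hour SBP results it cites are LS means against placebo, and nothing in SAP 4.1.1 or 7.1 is on that scale. The baseline-adjusted contrast cannot be recovered from the planned tables.

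The benefit of repair is real but modest. The half-widths rest on assumed SDs and correlation: about 8.5 to 12.7 mmHg unadjusted and about 7.2 to 12.2 mmHg adjusted, against cited effects of 14.2 to 16.7 mmHg. The repaired analysis gives a comparable estimate but only weak evidence of similarity. Neither document defines what counts as within the non-Japanese range, and Study 002's own model and handling of escape medication are not described, so full comparability remains an assumption.

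For AGT, the only gap is that the zilebesiran-placebo difference used to size the trial is never estimated.

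**What to change.** Add to SAP 7.1 a descriptive ANCOVA with arm and baseline value as terms, for 24-hour and office SBP and DBP. Report each dose-minus-placebo LS mean difference with a 95% CI and no p-value.

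- **Time points.** Make Month 3 the main comparison, because treat-to-target add-on therapy begins there (Protocol Table 3), and show Month 6 as supportive.
- **Datasets.** Run the model on both the all-collected and the escape-censored data, and name in advance which one is used for the comparison. This matters at Month 3 as well, since Protocol Table 3 allows some escape treatment before then.
- **Display.** Set the 24-hour SBP estimates beside the Study 002 values in Protocol 3.3. That section quotes no such values for DBP or office pressure, so those estimates stand alone.
- **AGT.** To close the smaller gap, add the Month 3 zilebesiran-minus-placebo difference in percent change with a 95% CI to SAP 8.1. At the planning SD of 0.42, the half-width would be about 30 points pooled or 36 points per dose.

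The cost is one standard model and some wording, made through the amendment route in SAP 1.1. It uses data already collected and leaves trial conduct unchanged. The drawback is that the intervals will be visibly wide, which is a fair picture of what 12 patients per arm can show.

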7.1.2 Summary of ABPM/OBP Censored by Concomitant Anti-Hypertensive Medication

Target population	:	Full Analysis Set
Analysis Items	:	SBP, DBP by ABPM and office blood pressure
Group	:	Placebo, Zilebesiran 300 mg, Zilebesiran 600 mg, Total zilebesiran, Overall Total
Time of analysis	:	Refer to section 2.8.1
Content of analysis	:	
 • Calculate the summary statistics of measurement value, change from baseline for each parameter by groups and analysis time points.

7.1.3 Summary of All Collected ABPM by Day/Night Time Measurements

Target population	:	Full Analysis Set
Analysis Items	:	SBP, DBP by ABPM
Group	:	Placebo, Zilebesiran 300 mg, Zilebesiran 600 mg, Total zilebesiran, Overall Total
Time of analysis	:	Refer to section 2.8.1
Content of analysis	:	
 • Calculate the summary statistics of measurement value, change from baseline for each parameter by groups and analysis time points day/night time.
Definition	:	
 • Daytime is defined as 6 am to 9:59 pm and nighttime is defined as 10 pm to 5:59 am.

7.1.4 Summary of ABPM ratio of Nighttime to Daytime Systolic Blood Pressure

Target population	:	Full Analysis Set
Analysis Items	:	SBP by ABPM
Group	:	Placebo, Zilebesiran 300 mg, Zilebesiran 600 mg, Total zilebesiran, Overall Total
Time of analysis	:	Refer to section 2.8.1
Content of analysis	:	
 • Calculate the number of patients and the percentages by groups and categories of SBP. • Category is as follows: < 0.9, 0.9 to < 1.0, >= 1.0, Missing

Definitions	:	
 • The denominator of proportions is the target population by groups. • Daytime is defined as 6 am to 9:59 pm and nighttime is defined as 10 pm to 5:59 am.
-------------	---	---

7.1.5 Treatment Responder in ABPM/OBP by Treatment and Visit

Target population	:	Full Analysis Set
Analysis Items	:	Reduction from baseline of ≥ 5 mmHg and ≥ 10 mmHg in SBP by ABPM/OBP
Group	:	Placebo, Zilebesiran 300 mg, Zilebesiran 600 mg, Total zilebesiran, Overall Total
Time of analysis	:	Refer to section 2.8.1
Content of analysis	:	
 • Count the number of patients for each analysis items by groups.
Definition	:	
 • The denominator of proportions is the target population by groups.

7.1.6 Summary of SBP and DBP assessed by HBPM

Target population	:	Full Analysis Set
Analysis Items	:	SBP, DBP by HBPM
Group	:	Placebo, Zilebesiran 300 mg, Zilebesiran 600 mg, Total zilebesiran, Overall Total
Time of analysis	:	Refer to section 2.8.1
Content of analysis	:	
 • Calculate the summary statistics of measurement value, change from baseline for each parameter by groups and analysis time points.

7.1.7 Spaghetti Plot of All Collected Systolic Blood Pressure/Diastolic Blood Pressure Assessed by 24-Hour ABPM/OBP during 6-Month DB period

Target population	:	Full Analysis Set
Analysis Items	:	SBP and DBP by ABPM/OBP
Group	:	Placebo, Zilebesiran 300 mg, Zilebesiran 600 mg
Time of analysis	:	Refer to section 2.8.1
Content of analysis	:	
 • Spaghetti Plot for measurement value and change from baseline of each analysis item by group, analysis visit in 6-Month DB period

7.1.8 Mean (+/- SEM) Change from Baseline in All Collected Systolic Blood Pressure/Diastolic Blood Pressure Assessed by 24-Hour ABPM/OBP during 6-Month DB period

Target population	:	Full Analysis Set
Analysis	:	SBP and DBP by ABPM/OBP

Items		
Group	:	Placebo, Zilebesiran 300 mg, Zilebesiran 600 mg
Time of analysis	:	Refer to section 2.8.1
Content of analysis	:	
 • Trend diagram of Mean \pm SEM will be presented graphically by groups, analysis visit in 6-Month DB period

7.1.9 Mean (+/- SEM) Change from Baseline in Censored Systolic Blood Pressure/Diastolic Blood Pressure Assessed by 24-Hour ABPM/OBP during 6-Month DB period

Target population	:	Full Analysis Set
Analysis Items	:	SBP and DBP by ABPM/OBP
Group	:	Placebo, Zilebesiran 300 mg, Zilebesiran 600 mg
Time of analysis	:	Refer to section 2.8.1
Content of analysis	:	
 • Trend diagram of Mean \pm SEM will be presented graphically by groups, analysis visit in 6-Month DB period

7.1.10 Proportion of Patients with Escape Antihypertensive Medication by Visit

Target population	:	Full Analysis Set
Analysis Items	:	Patients with Escape Antihypertensive Medication
Group	:	Placebo, Zilebesiran 300 mg, Zilebesiran 600 mg, Total zilebesiran, Overall Total
Time of analysis	:	Refer to section 2.8.3
Content of analysis	:	
 • The number of patients with Escape Antihypertensive Medication and the percentage will be calculated for each group.
Definition	:	
 • The denominator of proportions is the target population by groups.

8. Pharmacodynamic Evaluation

8.1 Summary of serum AGT

Target population	:	PD Analysis Set
Analysis Items	:	Serum AGT
Group	:	Placebo, Zilebesiran 300 mg, Zilebesiran 600 mg, Total zilebesiran, Overall Total
Time of analysis	:	Refer to section 2.8.1
Content of analysis	:	
 • Calculate the summary statistics of measurement value, change from baseline, percent change from baseline for each parameter by groups and analysis time points. • Calculate the summary statistics of maximum post-baseline percent change, time to Maximum post-baseline percent change (day) by groups.

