2.8 Analysis Visit

2.8.1 Analysis item except PK data, 24-hour Holter ECG Extraction

Assessment	Analysis item	Analysis visit
Efficacy	24-hour ABPM (SBP and DBP)	Baseline, Month 3, Month 6
	OBP (SBP and DBP)	Baseline, Day 2, Day 3, Day 8, Day 15, Month 1, Month 2, Month 3, Month 4, Month 5, Month 6, Month 9 and Month 12
	HBPM (SBP and DBP)	Baseline, Week X (at least once per week after Day 2)
Pharmacodynamic (PD)	Serum AGT	Baseline, Day 8, Day 15, Month 1, Month 2, Month 3, Month 6, Month 9 and Month 12
Biomarker	RAS (Renin concentration, Renin activity assessment and Aldosterone assessment)	Baseline, Month 1, Month 2, Month 3 and Month 6
Safety	Vital sign	Baseline, Day 2, Day 3, Day 8, Day 15, Month 1, Month 2, Month 3, Month 4, Month 5, Month 6, Month 9 and Month 12
	Weight, Height and BMI	Baseline and Month 6
	Single 12-lead ECG	Baseline and Month 6
	Hematology	Baseline and Month 6
	Serum Chemistry	Baseline, Day 8, Day 15, Month 1, Month 2, Month 3, Month 4, Month 5, Month 6, Month 9 and Month 12
	Liver Function Tests	Baseline, Day 8, Day 15, Month 1, Month 2, Month 3, Month 4, Month 5, Month 6, Month 9 and Month 12
	Urinalysis	Baseline and Month 6
	Coagulation	Baseline and Month 6
	Glycemic Assessment	Baseline
	Pregnancy Testing/FSH	Baseline
Optional research samples (urine, plasma, serum)	-	Baseline, Month 3 and Month 6
ADA	ADA and titer results	Baseline, Month 1, Month 3, Month 6

Abbreviations: ABPM=ambulatory blood pressure monitoring; ADA=anti-drug antibody;

AE=adverse event; AGT=angiotensinogen; DBP=diastolic blood pressure;

ECG=electrocardiogram; PD=pharmacodynamics; PK=pharmacokinetics; RAS = renin-angiotensin system; SBP=systolic blood pressure; DNA=deoxyribonucleic acid; FSH=follicle stimulating hormone;

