3.5.2 Time Windows

For tables and figures, the visit will be defined as the following:

- For actual visits on EDC except unscheduled visit, end of treatment visit, early termination visit and end of study visit, the visit will be used as it is for analysis.
- For actual visits on EDC of unscheduled visits, the data from this visit will be used to calculate baseline, worst post baseline, and maximum post baseline only. Post baseline unscheduled visits will not be considered for by-visit analysis.
- For actual visits on EDC of end of treatment visit, early termination visit and end of study visit, the analysis visit will be as the following table. The day of administration of the investigational drug is defined as “Day 1”

Analysis visit	Reference date	Time window
Day 8	Day 8	Day 5 ~ Day 11
Day 15	Day 15	Day 12 ~ Day 18
Month 1	Day 29	Day 24 ~ Day 34
Month 2	Day 57	Day 52 ~ Day 62
Month 3	Day 85	Day 78 ~ Day 92
Month 4	Day 113	Day 106 ~ Day 120
Month 5	Day 141	Day 134 ~ Day 148
Month 6	Day 169	Day 162 ~ Day 176
Month 9	Day 253	Day 239 ~ Day 267
Month 12	Day 337	Day 323 ~ Day 351

For all listings, the visit will be displayed as the visit on EDC.

4. Statistical Analysis

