4.1.4 Change from baseline and Percent change from baseline

The change from baseline and the percent change from baseline will be calculated using the following formula.

Change from baseline = Postdose value - Baseline value

$$\text{Percent of change(\%)} = \frac{\text{Postdose value} - \text{Baseline value}}{\text{Baseline value}} \times 100$$

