Content of analysis	:	
 • Create shift table for baseline data and post-dose visit data by analysis items and categories • Category is as follows: Worst Post-Baseline Value (msec): <=450, >450 to 480, >480 to 500, >500, Missing, Total Maximum Change from Baseline (msec): <=30, >30 to 60, >60, Missing, Total
Definitions	:	
 • If the patient performs the test but there is not assessment result data will be analyzed as “Missing” • The denominator of proportions is the target population by groups.

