12.4.6 Mean (+/- SEM) of Laboratory Parameters for Liver Function Tests/eGFR/Potassium by Visit

Target population	:	Safety Analysis Set
Analysis Items	:	Liver Function Tests, eGFR, Potassium (Refer to Appendix 2)
Group	:	Placebo, Zilebesiran 300 mg, Zilebesiran 600 mg
Time of analysis	:	Refer to section 2.8.1

Content of analysis	:	
 • Trend diagram of Mean \pm SEM of measurement value will be presented graphically by groups, analysis visit in 6-Month DB period and Safety/PD Follow-up
---------------------	---	--

12.4.7 eDISH Plot of Post-baseline Peak ALT or AST versus Total Bilirubin/ALT versus Total Bilirubin/AST versus Total Bilirubin, Per Patient

Target population	:	Safety Analysis Set
Analysis Items	:	AST, ALT, Total Bilirubin
Group	:	Placebo, Zilebesiran 300 mg, Zilebesiran 600 mg
Time of analysis	:	Refer to section 2.8.1
Content of analysis	:	
 • eDISH plot will be presented graphically by groups, patients. • The target of the analysis are patients who have post-baseline data
Definition	:	
 • Peak value is defined as the highest data of analysis item.

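### SAP 8.1, second bullet: the maximum of a percent change that is negative for a fall is each patient's weakest AGT suppression, not the peak reduction

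*SAP*

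**What the plan says.** SAP 8.1 has two content bullets for serum AGT. The first asks for summary statistics of the measured value, change and percent change at each analysis visit. The second adds a per-patient extreme: "Calculate the summary statistics of maximum post-baseline percent change, time to Maximum post-baseline percent change (day) by groups". It gives no direction, no absolute value and no tie rule. For timing, the section points to SAP 2.8.1, where the AGT visits are "Baseline, Day 8, Day 15, Month 1, Month 2, Month 3, Month 6, Month 9 and Month 12".

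The sign convention is in SAP 4.1.4: "The change from baseline and the percent change from baseline will be calculated using the following formula", followed by "Change from baseline = Postdose value - Baseline value". Percent change is that difference over the baseline value, times 100. There is no exception for AGT.

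The expected direction is in Protocol 3.3. For the 300 mg and 600 mg doses respectively in Study 002, "median reductions in serum AGT were 98.1% and 98.8% at Month 3 and 96.1% and 97.8% at Month 6".

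**The concern.** AGT is expected to fall by well over 90% on zilebesiran, so the percent changes at Months 3 and 6 will be large negative numbers. The maximum of a set of negative numbers is the one closest to zero. Followed exactly, the bullet selects the visit with the least suppression and reports its day as the time to maximum. A reader of the table would take those two figures for peak effect and time to nadir.

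Protocol 3.3 says the study is meant to help show that PD (serum AGT) is comparable in Japanese and non-Japanese patients. Depth and timing of the greatest reduction are natural descriptors for that purpose. Two programmers could also defend different tables from the same sentence.

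**Working it through.** **Is 'maximum' redefined anywhere?** The SAP states no figure for this summary, so there is nothing to reproduce. The first check is on usage.

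- SAP 3.5.2, on unscheduled visits: "the data from this visit will be used to calculate baseline, worst post baseline, and maximum post baseline only". Worst and maximum are listed as separate quantities, and maximum is not defined as a greatest reduction.
- SAP 12.3.3, on QTcF: "Maximum Change from Baseline (msec): <=30, >30 to 60, >60, Missing, Total". These categories describe the largest increase.
- SAP 12.4.7, on liver tests: "Peak value is defined as the highest data of analysis item". Again this is the algebraic high.
- Where the SAP means a fall it uses a word for one: reduction in 7.1.5, drop in 12.2.2, decrement in 12.2.3.

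No section turns maximum into nadir, minimum or absolute value for AGT.

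**Illustration from the documents' own figures.** Inputs are the Study 002 medians in Protocol 3.3. Visit days come from SAP 3.5.2: Month 3 is Day 85 and Month 6 is Day 169. The formula is (post - baseline)/baseline x 100. With baseline set to 100, a 98.1% reduction leaves 1.9, and (1.9 - 100)/100 x 100 = -98.1%. The other values follow in the same way.

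| Dose | Day 85 | Day 169 | Maximum as written | Greatest reduction (minimum) | Gap |
|---|---|---|---|---|---|
| 300 mg | -98.1% | -96.1% | -96.1%, Day 169 | -98.1%, Day 85 | 2.0 points |
| 600 mg | -98.8% | -97.8% | -97.8%, Day 169 | -98.8%, Day 85 | 1.0 point |

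**Adding onset and follow-up.** SAP 2.8.1 lists eight post-baseline AGT visits, from Day 8 to Month 12. The documents give no AGT values for Day 8 or Month 12. Assume, for illustration, -30% to -90% at Day 8 and -50% to -90% at Month 12 (Day 337). The literal maximum then lies between -30% and -90% and always falls on Day 8 or Day 337. The minimum stays at -98.1% or -98.8% on Day 85. This follows directly from assuming less suppression at those visits than at Month 6. The direction is plausible: Protocol Table 3 describes a gradual onset, and the medians are already weaker at Month 6 than at Month 3. The size is unknown.

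**Absolute value as an alternative.** Taking the largest absolute change gives the same answer as the minimum in the active-arm illustration. In placebo, where AGT may move either way, it could pick a rise in one patient and a fall in another, so the group summary would not describe a reduction.

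**The case against.** The best case against is that everyone will know what was meant. The protocol speaks of AGT reduction throughout, so maximum percent change probably means largest reduction, and a programmer may well code it that way. A literal result would also look odd beside the by-visit rows. That stands as a statement of intent, and the text does not prove what will be programmed. It does not rescue the wording, because the stated formula and the SAP's other uses of maximum and peak both point to the algebraic high.

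The objection to scope stands in full. A reader might infer that the secondary PD endpoint, or the Japanese versus non-Japanese comparison, is compromised. The documents do not support that. The endpoint is percent change at Month 3 and Month 6 (Protocol 2, SAP 1.2), and the first bullet of SAP 8.1 reports it at those visits. The plots in SAP 8.2 and 8.3 show percent change by visit. The non-Japanese AGT figures given for these doses in Protocol 3.3 are Month 3 and Month 6 medians, which the by-visit tables match directly.

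The objection to size also stands. Group medians at two visits do not yield a per-patient extreme over eight. A reader might conclude that the time to nadir would be wrong by 84 days, but 169 - 85 = 84 is only the spacing of the two visits that have figures. Nothing in the documents shows that individual nadirs fall at Month 3. Likewise, recasting the 300 mg gap as residual AGT (3.9% against 1.9%) makes it look twofold, but SAP 8.1 does not report residual AGT.

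**Conclusion.** The point holds for one supplementary bullet. Under the sign convention in SAP 4.1.4, the second bullet of SAP 8.1, if followed exactly, returns each patient's weakest suppression and its day. In placebo it returns the largest rise or, if every value is below baseline, the smallest fall. For a summary meant to show peak effect that is a wrong result, not merely missing detail.

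The only size the documents support is illustrative: 2.0 points for 300 mg and 1.0 point for 600 mg, from Study 002 medians at two visits. Early and follow-up visits could make it larger, by an amount that cannot be stated. The conclusion rests on the literal wording; the intended statistic was probably the greatest reduction. The effect on the study's main conclusions is small, since analyses are descriptive (Protocol 7.2) and every other AGT output is unaffected. The correction is still worth making because it is nearly free.

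**What to change.** Replace the second bullet of SAP 8.1 with wording to this effect: *summary statistics of the maximum post-baseline percent reduction (the minimum, ie most negative, post-baseline percent change) and of the time to its first occurrence (days), by group.*

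State the visit window, and say whether unscheduled samples count, since SAP 3.5.2 admits them to maximum post-baseline values. SAP 8.2 and 8.3 already separate the 6-month double-blind period from double-blind plus follow-up, so the same labels can be used. Restricting the summary to the double-blind period is optional; it is not needed to correct the sign.

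The cost is one line of SAP text and one programming rule, with no new data. SAP 1.1 already provides the route: an amended version with revision history.
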